Appendix A: Power Analysis

Power and Significance Level

[figure not shown]
These are set to standard,

Power = 0.8

Significance Level (alpha) = 0.05

Metric	Effect Size used in calculation	Required sample size when comparing participants' sessions (paired sample)	Required sample size when comparing group A to group B
WOMAC - Function bivariate	0.71 ²⁷	18	32
WOMAC - Pain bivariate	0.41 ²⁷	49	94
WOMAC - Function Standing/Walking bivariate	0.45 ²⁷	41	78

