A sample size of 32 participants was calculated to be sufficient for a two-tailed significance level of 5% and a power of 80% (Appendix A). This was adjusted to 45 participants with knee osteoarthritis to allow for dropouts. Recruitment for this study will be conducted using a recruitment flyer and through the CIONIC website. Recruitment will be based on a first come

basis. Interested participants will complete a questionnaire to be reviewed according to the inclusion and exclusion criteria. Responses will then be reviewed, and prospective participants will be invited to schedule a virtual meeting with a study staff member who will screen the prospective subject for an understanding of the study and for their voluntary participation. All participants will be assigned a unique number using a computer random number generator and randomly assigned to a group by a researcher. All participants will receive their assigned intervention at their first lab visit.

Inclusion Criteria

- Persons with knee osteoarthritis between the ages of 22 and 75
- Ability to walk a duration of 30 minutes per walking session (with or without an assistive device), for three days per week
- Able to tolerate the device for up to 1 hour per lab session
- No recent change in medication or exacerbation of symptoms over the last 60 days
- Radiographic KOA K&L grade 2 or 3 or physician diagnosed mild or moderate KOA if radiographic imaging is not available
- No hyaluronic acid or cortisone injection into knees in previous 12 months

Exclusion Criteria

- Lower motor neuron disease or injury (e.g. peripheral neuropathy) that may impair response to stimulation
- Absent sensation in the impacted or more impacted leg

- Inadequate response to stimulation, as defined as inability to achieve muscle contraction or tolerate stimulation
- Inability to ambulate with the sleeve in place of an ankle foot orthosis (AFO)/knee ankle foot orthosis (KAFO) if utilized
- Use of FES devices in the past year
- Demand-type cardiac pacemaker or defibrillator
- Malignant tumor in the impacted or more impacted leg
- Existing thrombosis in the impacted or more impacted leg
- Fracture or dislocation in the impacted or more impacted leg that could be adversely affected by motion from stimulation
- History of knee surgery
- History of other types of arthritis
- History of neurological disease
- History of seizures or diagnosed with epilepsy/seizures
- Current pregnancy

Methodology

Overview of Study

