This study is a randomized controlled trial. Figure 2 depicts a flow diagram of the study design. Participants will be screened for eligibility through a questionnaire, and after study details are explained and consent is obtained, they will be invited to the study site. Assessments will be conducted at CIONIC Inc., and involve approximately 45 patients for a 12 week study period.

CIONIC

CIONC FOR ORTHOPEDICS

All subjects will be assigned an electrical stimulation system to wear on the most impacted leg and be prescribed a home-based exercise and walking program. Subjects will be randomly assigned into three groups: (a) control; (b) NMES+; (c) NMES+FES. The control group will not receive stimulation for the exercise and walking program, whereas subjects in NMES+ will receive stimulation during exercises, and subjects in the NMES+FES group will receive stimulation during exercises and walking. Outcome measures will be assessed at baseline, 6 weeks after baseline, and end of study (Table 2). Equipment and additional feedback will be collected at the end of study. These three groups will be analyzed using several outcome measures. Primary outcome measures of the study are quadriceps strength, perceived functional capacity, self-reported pain, and walking performance. Secondary interest will be adherence to program, thigh muscle volume, functional ability of the lower limb, and quality of life. The CIONIC system will be used to track adherence (duration of sessions, frequency of use).

[figure not shown]

Figure 2: Study flow

Table 2: Study overview

Comparison Groups	Treatment Schedule	Timing and Outcome Measures
Control (unstimulated exercise and walking)	Exercise: 5x/week for 12 weeks Progression every 3 weeks	At baseline, midpoint and end of study: Quadriceps strength Perceived functional capacity Self-reported pain Walking performance Thigh muscle volume Functional ability of lower limb Quality of life EMG activity
NMES+ (NMES+exercise and unstimulated walking)	Walking: 10 min, 3x/week for 12 weeks Progression up to 30 min by end of study	Weekly: Adherence to program
NMES+FES (NMES+exercise and FES+walking)		

Participant Identification, Recruitment & Informed Consent

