Other information to be collected include date of birth, gender, ethnicity, height, weight, duration of condition, and type and dosage of medication.

Data Analysis/Statistical Analysis

For each of the primary and secondary measures, we will perform a Shapiro-Wilk test for normality to assess the assumption of normality. If the outcome variable is approximately normally distributed, a paired t-test will be used to statistically compare outcome metrics before and after the intervention within a condition. If the normality assumption is not met, the Wilcoxon signed rank test will be used as an alternative to the paired t-test for this statistical comparison. Bonferroni multiple hypothesis correction will be utilized for a corrected significance level.

To compare across conditions, an analysis of variance (ANOVA) test will be performed if the outcome variable is normally distributed. If the normality assumption is not met, the Kruskal Wallis test will be used as the non-parametric version of ANOVA. We may also employ a repeated measures ANOVA test for inclusion of all three timepoints.

Organizational Relationships

CIONIC works closely with Edge Analytics, a consulting firm who has been contracting for CIONIC for over two years. The firm is primarily responsible for algorithm development and statistical analyses of kinematic and EMG data. [name], [name], and [name] are employees of Edge Analytics who have been working closely with Cionic. [name] is a sub-investigator on this study.

Risk & Benefit Assessment

The Cionic Neural Sleeve has been tested extensively in previous studies. Across these prior studies, the Cionic Neural Sleeve has been evaluated for walking and exercise mode, approved for FDA 510k submission and its intended use in a simulated home environment, and for home usability with no adverse events.

However, any study of this kind comes with some known risks, that although rare, are associated with participation:

- Discomfort from the electrical stimulation
- Minor skin irritation at the sites of sensor/electrode pad placement
- Muscle fatigue from prolonged device use
- Anxiousness due to the anticipation of receiving an electrical stimulation
- Injury caused by unintended falls while using the Cionic Neural Sleeve
- Exposure to coronavirus disease 2019 (COVID-19) or other communicable disease

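### Appendix A's paired requirement of 18 is a one-group number: three within-arm tests would need 54 complete pairs, and 45 enrolled cannot put 18 in every arm

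*Combined protocol and SAP*

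**What the plan says.** Appendix A (Power Analysis) sets power at 0.8 and "Significance Level (alpha) = 0.05" once, above a table with two sample-size columns. The first is headed "Required sample size when comparing participants' sessions (paired sample") and lists 18 for WOMAC-Function (effect 0.71), 49 for WOMAC-Pain (0.41) and 41 for the WOMAC standing/walking function item (0.45). The second is headed "Required sample size when comparing group A to group B" and lists 32, 94 and 78 for the same effects.

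Participation Selection and Randomization states: "A sample size of 32 participants was calculated to be sufficient", at a two-sided 5% level and 80% power, with a reference to Appendix A. The number is then raised to 45 to cover dropouts. No dropout rate is given.

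Overview of Study has three arms: "Subjects will be randomly assigned into three groups: (a) control; (b) NMES+; (c) NMES+FES". No allocation ratio is given.

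Data Analysis/Statistical Analysis says that, for normally distributed outcomes, "a paired t-test will be used to statistically compare outcome metrics before and after the intervention within a condition". Comparisons across conditions are described separately, by ANOVA or Kruskal-Wallis. A Bonferroni correction is promised without a count of tests.

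**The concern.** Appendix A sizes two kinds of comparison at 80% power, and the paired one is the first analysis that the statistical section names, for every primary and secondary measure. That test is run arm by arm, yet the plan never relates the 18 to the size of an arm. A reader who sees 18 next to a trial of 32 or 45 may assume that the paired tests are well covered.

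If they are not, a non-significant change within an arm carries less information than Appendix A implies. At 80% power the assumed effect is missed 20% of the time. On Appendix A's own effect it would be missed about 28% of the time with 15 per arm (100 − 72.5), and 43–48% of the time with 10–11 (100 − 56.6 and 100 − 51.8). A pattern in which one arm improves significantly and another does not could then easily arise by chance.

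**Working it through.** **Inputs.** Two-sided alpha 0.05 (Appendix A; two-sidedness from Participation Selection and Randomization). Power 0.80 and effects 0.71, 0.41 and 0.45 (Appendix A). Three arms (Overview of Study). 45 enrolled, 32 called sufficient. Assumed: equal allocation, giving 45/3 = 15 and 32/3 = 10.7, so 10–11 per arm.

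**Step 1: reproduce the printed figures.** For a paired t-test on n complete pairs with standardised mean change d, power is the probability that a noncentral t variable with n − 1 degrees of freedom and noncentrality d√n falls outside ± t(0.975, n − 1). Solving for 80% power gives:

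| Effect | Required n | Printed |
|---|---|---|
| 0.71 | 17.59 | 18 |
| 0.41 | 48.65 | 49 |
| 0.45 | 40.72 | 41 |

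All three match. The alternatives do not: for 0.71 a normal approximation gives 15.6 and a one-sided t-test 13.7. The printed numbers are therefore complete pairs in one group.

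**Step 2: apply to three arms.** 3 × 18 = 54, which exceeds 45. No split of 45 puts 18 in all three arms, whatever the allocation ratio and even with no dropout.

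**Step 3: power at the available arm sizes, unadjusted two-sided 5%.**

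| n per arm | d√n at 0.71 | Power at 0.71 | Effect detectable with 80% power |
|---|---|---|---|
| 18 | 3.01 | 81.0% | 0.70 |
| 15 | 2.75 | 72.5% | 0.78 |
| 11 | 2.35 | 56.6% | 0.94 |
| 10 | 2.25 | 51.8% | 1.00 |

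**Step 4: the other listed effects.** At 15 per arm, power is 31.6% for 0.41 and 36.9% for 0.45. At 10–11 it is 21–23% and 25–27%.

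**Step 5: Bonferroni.** The number of tests is not stated, so the counts here are assumed. At 0.71 and 15 per arm, three tests (alpha 0.05/3) give 53.0% and four tests (0.05/4) give 47.9%.

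**Step 6: sensitivity to the meaning of 0.71.** Appendix A uses one value for both columns. If it is standardised by the between-person SD, the paired effect is 0.71/√(2(1 − r)), where r is the before-after correlation, which the plan does not give. At 15 per arm, unadjusted:

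| r (assumed) | Paired effect | Power |
|---|---|---|
| 0.4 | 0.65 | 65% |
| 0.5 | 0.71 | 72.5% |
| 0.6 | 0.79 | 81.5% |
| 0.7 | 0.92 | 91% |

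At 11 per arm and r = 0.7, power is 78%.

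**The case against.** Four objections have force.

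- **The 80% statement in the recruitment section is not about these tests.** The 32 to which it is attached is Appendix A's two-group figure for WOMAC-Function. A reader might infer that the protocol claims 80% power for the within-arm tests at 32 or 45; it does not say so. What stands is narrower: Appendix A's power of 0.8 governs its paired column too, and the design cannot deliver it in all three arms.
- **72% is not a ceiling.** Step 6 shows that a correlation above 0.5 would raise it if 0.71 is a between-person standardised effect. The documents do not say which SD underlies it. Appendix A nevertheless enters 0.71 in the paired calculation, so 72% is what its own inputs imply. Nor is it shown that every arm falls short of 18: a split such as 18, 18 and 9 would bring two arms up to it.
- **32 is not a forecast of completers.** It is the size called sufficient, and 45 is a margin above it. The 52–57% range describes what happens if retention falls to that size (a loss of 1 − 32/45 = 28.9%), not what the plan expects.
- **The within-arm tests are not the main question.** The research objectives and hypotheses chiefly compare stimulated with unstimulated groups, and no rule requires significant change in all three arms. This limits the weight of the point but does not remove it, since Appendix A sizes the paired comparison explicitly. How the two-group 32 should be read is a separate matter, and settling it by wording alone would leave the paired column unlabelled.

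**Conclusion.** The point holds in this form: Appendix A's 18 is a per-arm number of complete pairs, the analysis needs it three times over, and 45 enrolled cannot supply 54. That conclusion does not depend on the allocation ratio.

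The size of the shortfall does rest on assumptions. With equal allocation, a paired effect of 0.71 and unadjusted 5% tests, power per arm is about 72% at 15 and 52–57% at 10–11. It is lower once the planned Bonferroni correction is applied, and much lower for the other two listed effects. It could be higher if the paired effect exceeds 0.71. The figures are for the t-test; the plan's Wilcoxon alternative was not evaluated.

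This should be corrected, but it is a matter of stating power honestly and does not undermine the randomised comparison.

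**What to change.** 1. In Appendix A, label the paired column *complete pairs per arm*, and state that the planned arm size does not reach it in all three arms.
2. In Participation Selection and Randomization, add that the 80% figure does not apply to the within-condition tests, and give the achieved values. For example: *Assuming equal allocation and an unadjusted two-sided 5% level, the within-arm before-after test of WOMAC-Function has about 72% power for a paired effect of 0.71 with 15 complete pairs per arm, and 52–57% with 10–11. The paired effect detectable with 80% power is 0.78 and 0.94–1.00 respectively. Power is lower at the Bonferroni-corrected level, given here for the number of tests specified in the analysis section.* The sponsor needs to supply that number.
3. State the allocation ratio, and whether 0.71 is scaled by the SD of change or by the between-person SD.
4. In Data Analysis/Statistical Analysis, report within-arm changes with 95% confidence intervals, and state that a non-significant within-arm test will not be read as absence of change.

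The cost is a few sentences and a less favourable power statement. No extra participants, visits or measurements are needed.

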Acknowledging the benefits of combined electrotherapy and KOA as a progressive and degenerative condition with unlikely regression or restoration of damaged structures, the study aims to investigate the effects of stimulation assisted activities to delay the disease progression and muscle atrophy in those with KOA. Thus, the purpose of this research is to investigate if stimulation assisted (NMES and FES) activities can combat disuse atrophy for individuals diagnosed with KOA. This study will use a home-based medical device (Cionic Neural Sleeve NS-100, K213622, CIONIC, San Francisco, CA) to administer electrical stimulation and measure its effect on outcomes that include quadriceps strength, perceived functional capacity, pain, and walking performance.

Significance

Adults with KOA spend most of their day engaging in sedentary behavior and report worse physical function⁸, which may lead to progression of the condition, increased functional dependence and decreased quality of life²². Existing literature shows that NMES assisted exercise may counter disuse atrophy in sedentary individuals²³, but because there has been minimal research investigating the effects of FES in the KOA community, exploration of this study is warranted.

Figure 1: Cionic Neural Sleeve system

Note: Left: Cionic Neural Sleeve showing the configuration of the FES and electromyographic (EMG) electrode arrays. Center: Cionic mobile application interface for setting FES parameters (frequency, pulse width, intensity) and current field steering. Right: Cionic Neural Sleeve on body.

Research Objectives

1. Analyze the effects of electrical stimulation assisted interventions versus a conventional exercise program on muscle strength, perceived function, and pain in KOA.
2. Compare the effects of unassisted walking and stimulation assisted walking on walking performance in KOA.
3. Measure the compliance of electrical stimulation assisted interventions to a conventional exercise program on the effects of pain and perceived function in KOA.

Hypotheses

It was hypothesized that combined electrotherapy groups will show larger muscle mass and strength improvements; improved gait kinematics, pain and perceived function; and a high compliance to the assigned program compared to the unstimulated group.

Specific Aims

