All participants will be prescribed the same exercise program and instructed to adhere to the program for 5 days per week for 12 weeks, for a total of 60 exercise sessions. This program requires isometric quadriceps contractions in a supine position with a rolled-up towel placed behind the knee. For this study, subjects will contract their thigh muscle to straighten their knee for three seconds and relax for three seconds for a repetition, as prompted by the supporting app. Participants in this study will be instructed to perform sets of 10 repetitions, with a progression every 3 weeks (Table 3). For exercise sessions requiring more than 1 set, the sets should be separated by 30-second rest intervals.

Table 3: Exercise Program

Exercise	Frequency	Progression
Isometric quadriceps contraction	5 days per week	Weeks 1-3: 1 set of 10 Weeks 4-6: 2 sets of 10 Weeks 7-9: 3 sets of 10 Weeks 10-12: 2 sets of 10, twice per day

Walking Program

All participants will be prescribed the same walking program, where subjects will be instructed to walk 3 days per week for 12 weeks, for a total of 36 walking sessions. At the start of the study, participants will walk for 10 minutes and then gradually increase walking time up to 30 minutes per walking session by the end of the study.

Electrical Stimulation System

Electrical stimulation will be given using the Cionic Neural Sleeve, a wearable single channel stimulator with a monophasic rectangular pulse. The Cionic Neural Sleeve system consists of a Nylon/Lycra garment equipped with small metal electrodes covered by reusable 1.75" x 1.75" electrode pads that adhere to the skin's surface and a Control Unit. Small wires are routed through the interior of the sleeve from each metal electrode and electrode pad to a handheld removable Control Unit that houses the central computing module and battery. There are flaps on the upper and lower leg that are secured in place with Velcro, and an upper thigh pocket to hold the Control Unit. The Control Unit connects to the sleeve via a short connector located in the upper thigh pocket and communicates with a smartphone via the CIONIC application using Bluetooth™ Low Energy (BLE). The device is a Food and Drug Administration (FDA)-cleared Class 2 medical device.

Study Removal and Device Returns

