1. Performing routine exercise (with or without stimulated assistance) has been shown to improve general health, strength, and pain.
2. Walking with a stimulation device may facilitate neural retraining which could result in improved motor control, pain, and walking performance. Although this has been anecdotally reported in previous studies, CIONIC hopes to establish this with clinical endpoints in this study.
3. If requested, CIONIC will provide the participant with a copy of their data, which the participant may choose to share with members of their clinical team to support their care. CIONIC is not a medically licensed company and cannot and will not provide medical advice; however, CIONIC will explain the data in more detail to the participant if requested.

Study Withdrawal

During the consent process, participants will be informed that they may withdraw from the study at any time. The study team member responsible for reviewing informed consent will confirm that they understand that they have this option. Participants will be entitled to financial compensation for each lab visit. The investigators or sponsors may stop the study or take participants out of the study at any time should they judge that it is in their best interest, if subjects experience a study-related injury, if subjects need additional or different medication/treatment, or if they do not comply with the study plan. The researchers may remove participants from the study for various administrative and medical reasons. Participants will not be compensated for lab visits that they cancel or miss.

Data Storage, Monitoring and HIPAA

This study involves the collection of data from sensors on the Cionic Neural Sleeve system, and possibly external kinematic data collection systems for validation. Data collected will not include personally identifiable information. The devices comprising the system connect wirelessly via BLE to an application running on a smartphone or iPad.

CIONIC's smartphone or iPad's camera will also record video of the lower body at the lab visits. The participant's face and voice will not be recorded. The content of the data will be uploaded to a secure server. Each set of data will be organized using a unique numerical identifier that does not include protected health information (PHI) (e.g., initials) will be stored in our Health

Insurance Portability and Accountability Act (HIPAA) compliant database with access limited to

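### Appendix A uses one undefined effect size, 0.71, for both the before-after and the between-arm sample size, so the stated 80% power is not supported for stimulation against an exercising control.

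*Combined protocol and SAP*

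**What the plan says.** The section on participant selection and randomization states "A sample size of 32 participants was calculated to be sufficient for a two-tailed significance level of 5% and a power of 80" per cent, then raises the number to 45 for dropouts. The source is Appendix A, which sets 80% power and "Significance Level (alpha) = 0.05". Its table has a single column, "Effect Size used in calculation", followed by two sample-size columns: one for paired sessions and one headed "Required sample size when comparing group A to group B". The row "WOMAC - Function bivariate" gives 0.71, credited to reference 27, with 18 in the paired column and 32 in the between-group column.

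The first research objective is to "Analyze the effects of electrical stimulation assisted interventions versus a conventional exercise program on muscle strength, perceived function, and pain in KOA". The comparator is active. Under Exercise Program, "All participants will be prescribed the same exercise program", and the walking programme is likewise common to all arms. The overview of the study shows that control participants differ only in receiving no stimulation.

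The plan expects exercise alone to help. The Benefits section says "Performing routine exercise (with or without stimulated assistance) has been shown to improve general health, strength, and pain". The introduction also credits exercise with better physical function, the domain behind the 0.71.

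**The concern.** A participant's change from baseline and the difference between two arms are different quantities. They can share one standardised value, but only under conditions that the plan should state. Where the comparator is itself expected to work, the between-arm difference is what remains after the control arm's improvement is taken off.

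Objective 1 rests on the randomised between-arm comparison, so this is where the power statement matters most. If 80% is taken at face value, a non-significant result would be read as good evidence that stimulation adds nothing to exercise. The trial may in fact be able to detect only a very large added effect.

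**Working it through.** **Inputs.** From Appendix A: effect sizes 0.71, 0.41 and 0.45; alpha 0.05; power 0.80. From the selection and randomization section: two-sided testing, 32 required, 45 enrolled. From the study overview: three groups. Not given, so assumed: equal allocation (15 per arm), a common SD of change, and the fraction f of 0.71 that controls gain through exercise alone.

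**Reproducing the table.** Paired: n ≈ (1.960 + 0.842)²/d², solved with the t distribution. Two-sample: n per group ≈ 2(1.960 + 0.842)²/d². For d = 0.71 the normal formula gives 2 × 7.849/0.5041 = 31.1, so 32 per group.

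| d | Paired, t-test | Table | Two-sample per group, t-test | Table |
|---|---|---|---|---|
| 0.71 | 17.6 | 18 | 32.1 | 32 |
| 0.41 | 48.6 | 49 | 94.4 | 94 |
| 0.45 | 40.7 | 41 | 78.5 | 78 |

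All six entries reproduce, with the same d in both columns and the between-group figure read as a number per group. As two-group totals they would be 64, 188 and 156, which do not match.

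**Reading 1: 0.71 is the stimulated arm's own gain.** On change scores with a common SD, the between-arm effect is 0.71 × (1 − f). For example, f = 25% gives 0.71 × 0.75 = 0.53.

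| Assumed f | Between-arm d | Power at 32 per group | n per group for 80% (t-test, unrounded) | Power at 15 v 15 |
|---|---|---|---|---|
| 0 | 0.71 | 80% | 32.1 | 47% |
| 10% | 0.64 | 71% | 39.4 | 39% |
| 25% | 0.53 | 55% | 56.3 | 29% |
| 50% | 0.355 | 29% | 125.5 | 16% |

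The 32-per-group column isolates the effect of control improvement. The last column adds the smaller arms. Its 47% at f = 0 is due to arm size alone, a separate matter that arises because a per-group 32 is treated as the trial total.

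If end values rather than changes are compared, the scale matters too. With no control change, d = 0.71 × √(2(1 − r)), where r is the baseline-to-end correlation. The two columns share 0.71 only at r = 0.5. An assumed r = 0.7 gives d = 0.55 and 58% power at 32 per group.

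**Reading 2: 0.71 is a target advantage over control.** Controls may then improve by any amount, and 32 per group does give 80% power. Stimulated participants must, however, gain 0.71 SD on top of what exercise gives. No section of the plan argues for an added gain of that size.

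**What the planned size can detect.** Two-sided unadjusted two-sample t-test, 80% power, equal allocation:

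| Completers | One stimulated arm v control | Both stimulated arms pooled v control |
|---|---|---|
| 45 | 15 v 15: 1.06 SD | 30 v 15: 0.91 SD |
| 32 | 10.67 v 10.67: 1.28 SD | 21.33 v 10.67: 1.09 SD |

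The second row is the plan's own dropout case: 1 − 32/45 = 28.9% lost.

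**The case against.** The best defence is that the table simply lists, for each metric, the number needed to detect a given effect under two alternative designs. On that view 0.71 is a target and predicts nothing about either arm.

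This stands in part. A reader might infer that Appendix A requires the control arm not to improve. The documents do not establish that: it follows only if 0.71 is the stimulated arm's own gain. A reader might also infer that a stimulated-arm change above 0.71 would contradict the paired column. It would not, because a larger change only raises paired power. Nor is there an arithmetic error, since every entry follows from its input.

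The sources do not settle which reading was meant. The title of reference 27 speaks both of clinically important differences and of rehabilitation. The outcome section takes a benchmark for improvement of 14.48 from that reference, but nothing links it to 0.71. Appendix A also contains a figure that was not readable for this review; if it defines the effect size, that part of the point falls away.

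The evidence that controls will improve is qualitative. The Benefits sentence names general health, strength and pain, not function; the introduction does name function, but without a size. The values of f are therefore illustrative.

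The defence does not rescue the power claim. As a target, 0.71 SD over an active exercise programme still needs a justification, and none is given.

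**Conclusion.** The concern holds as an unsupported design assumption. One effect size serves two different quantities, and the plan does not say what it represents, how it is standardised or what change the control arm is assumed to make. If it is the stimulated arm's own gain, power at 32 per group falls from 80% to about 71%, 55% or 29% when controls obtain 10%, 25% or 50% of that gain. If it is an advantage over exercise, the size of the advantage is not argued for. Under neither reading is the 80% claim supported for Objective 1.

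The power figures rest on a two-sided two-sample t-test at 5%, a common SD of change and an assumed f. The low power at 15 per arm should not be attributed to control improvement alone, since much of it comes from arm size.

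**What to change.** In Appendix A, state what 0.71 represents and which SD standardises it, without presuming that it suits the paired column. Define the between-group effect as the difference in change between a stimulated arm and the exercise-and-walking control, and show power over a range of control-arm change, for example 0, 25% and 50% of 0.71.

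In the selection and randomization section, replace the 80% claim for the between-arm comparison with the smallest added benefit detectable at 80% power: about 1.06 SD pairwise if all 45 complete and about 1.28 SD if 32 complete, with the assumptions given. The analysis section plans ANOVA or Kruskal-Wallis across the three arms and no pooled contrast. If one is added, the figures are about 0.91 and 1.09 SD.

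Add that Bonferroni correction of these comparisons would raise all four figures, and that a non-significant between-arm result does not rule out a smaller added benefit over exercise.

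The cost is rewording and a less favourable stated power. No extra participants or procedures are needed.
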